1.1 SYNOPSIS

Title:	Phase II Trial of Liraglutide (Saxenda®, Novo Nordisk) in Adolescents with Obesity After Sleeve Gastrectomy: A Pilot Open-Label Study
Study Description:	This trial is an open-label Phase II non-randomized pilot study conducted at the NIH Clinical Center to investigate the efficacy of daily subcutaneous injection of liraglutide, a glucagon-like peptide-1 (GLP1) analogue to promote reduction of body mass index (BMI) in adolescents who continue to have obesity (BMI ≥ 30 or BMI $\geq 95^{\text{th}}$ percentile for age and sex) 1 year or more after vertical sleeve gastrectomy (SG). We hypothesize that administration of liraglutide will be associated with reduction in BMI in such adolescents.
Objectives:	
Primary objective: To determine the effect size for the change in BMI of liraglutide 3.0 mg daily subcutaneously at 16 weeks in adolescents who have obesity after SG, in order to use the observed changes to determine the sample size of a subsequent randomized, controlled investigation.
 
Hypothesis: The Primary Endpoint is estimation of required sample size for a later randomized controlled trial through calculation of effect size for change in body mass index (BMI) from baseline to 16 weeks of liraglutide. The hypothesis is: The data will be sufficient to calculate the effect size for change in BMI from baseline to 16 weeks for a 2-group experiment (placebo versus liraglutide).
 
Secondary objectives:
 
To study the effects of 16 weeks of liraglutide 3.0 mg subcutaneously on change in mean BMI and fat mass in adolescents who underwent vertical sleeve gastrectomy (SG) ≥ 1 year prior to study initiation but still have obesity or have a recrudescence of obesity despite surgery.
 
To compare the effects of liraglutide on BMI and fat mass in enrolled participants who had a poor initial response to SG (<20% BMI reduction at BMI nadir) vs. those with a typical post-SG weight loss ($\geq 20\%$ BMI reduction at BMI nadir).
 
Additional Objectives:
 
To examine the effects of daily subcutaneous liraglutide in enrolled participants on changes in body composition, metabolic syndrome markers, energy intake, glucose tolerance, gastrointestinal (GI) hormone concentrations, appetite, free living physical activity, mood,

Abbreviated Title: Liraglutide in Teens Post-SG

Version Date: 1/30/23

suicidality, weight related quality of life, self-perception of body image, and secretome.

Endpoints:

Primary Endpoint: Estimation of required sample size for a later RCT through calculation of effect size for change in body mass index (BMI) from baseline to 16 weeks of liraglutide.

Key Secondary Endpoints:

Changes in BMI and fat mass after 16 weeks of liraglutide

Comparison of changes in BMI and fat mass after 16 weeks of liraglutide in participants who had a poor initial response to SG (<20% BMI reduction at BMI nadir) vs. those with a typical post-SG weight loss ($\geq 20\%$ BMI reduction at BMI nadir)

Tolerability and safety of liraglutide 3.0 mg.

Additional (exploratory) Endpoints: Change from baseline to 16 weeks of liraglutide in:

1. Proportion reducing BMI by at least 5% and 10%
2. BMI standard deviation score for age and sex (BMIZ)
3. Body weight
4. Percentage total body fat mass by DXA
5. Appetite score using visual analog scale (VAS)
6. Attention bias to highly palatable images
7. Energy intake at buffet meal
8. Free living physical activity by accelerometry
9. Metabolic syndrome markers (waist circumference, systolic and diastolic blood pressure, lipids, fasting plasma glucose level)
10. Fasting plasma insulin and HOMA-IR index
11. 2-hour oral glucose tolerance test (OGTT) insulin and glucose measurements
12. Hemoglobin A1C
13. Plasma GI hormones (GLP-1 and PYY) during OGTT
14. Weight related quality of life (QoL) score
15. Beck Depression Inventory total score
16. Body-Esteem Scale Score for Adolescents and Adults
17. Columbia Suicide Severity Rating Scale
18. Secretome analysis
19. Stool microbiome analysis

Study Population:

Up to a total of 50 male and female adolescents age < 21 years old from Washington D.C., Maryland, and Virginia who underwent SG at least 1 year prior to enrollment and have BMI ≥ 30 kg or $\geq 95^{\text{th}}$

Abbreviated Title: Liraglutide in Teens Post-SG

Version Date: 1/30/23

percentile for age and sex in order to enroll at least 40 who are eligible and agree to take liraglutide for 16 weeks.

Phase:

Phase II

Description of Sites/Facilities

We will primarily recruit participants who previously underwent SG from Children's National Hospital (CNH), in Washington, DC, a high-volume pediatric bariatric surgery center in our area.

Enrolling Participants:

Participants will be assessed at the NIH Clinical Center for all study visits. Eligible participants may also be interviewed by telephone.

Description of Study Intervention:

Eligible patients will be treated with daily subcutaneous liraglutide (starting at 0.6 mg daily with weekly dose escalations up to 3.0 mg per day or max tolerated dose) for up to 16 weeks.

Study Duration:

36 months

Participant Duration:

7 months (28 weeks)

[figure not shown]
(16 weeks on Study Drug and 12 weeks off Study Drug)

Abbreviated Title: Liraglutide in Teens Post-SG

Version Date: 1/30/23

1.2 SCHEMA

Flow diagram of open label trial

1.3 SCHEDULE OF ACTIVITIES (SOA)

Procedures		Phone Screen - ≤ 4 wks before baseline	Screening Visit	Study Visit 1 Day 0	Study Visit 2 Day 28 +/- 10 days	Study Visit 3 Day 56 +/- 10 days	Study Visit 4 Day 84 +/- 10 days	Study Visit 5 Day 112 +/- 10 days	Final Study Visit 6 Day 196 +/- 10 days
Informed consent		X							
Demographics	X	X							
Medical history	X	X							
Nutrition Counselling ¹			X	X	X	X	X	X	
Injection Teaching				X					
Administer study intervention ²				X				X	
Concomitant medication review	X		X					X	
Physical exam (including height and weight) ³		X	X	X	X	X	X	X	X
Waist circumference ⁴			X					X	X
Vital signs ⁵		X	X	X	X	X	X	X	X
Pregnancy test ⁶		X	X	X	X	X	X	X	
Screening labs (CBC, A1C, acute care panel, hepatic panel, mineral panel, ESR, CRP, 25-OH vitamin D, PT, PTT, urinalysis)		X							
Adverse event review and evaluation				X				X	
DXA				X				X	
Metabolic syndrome markers ⁷			X					X	
2-hour Oral glucose tolerance test (OGTT)			X					X	
Blood draw (Hb A1C, Plasma GI hormones: GLP-1, PYY, research samples to be saved)			X					X	
Stool sample collection (optional)			X					X	
Energy intake at buffet meal			X					X	
Appetite score pre and post meal using visual analog scale (VAS)			X					X	
Attention bias to palatable images study		X					X		
Free living physical activity by accelerometry set -up		X					X		
Weight related quality of life (QoL) score			X					X	
Beck Depression Inventory			X					X	
Columbia Suicide Severity Rating Scale			X					X	
Body-Esteem Scale			X					X	
Blood Sample for Secretome Analysis			X					X	

Abbreviated Title: Liraglutide in Teens Post-SG

Version Date: 1/30/23

Complete Case Report Forms (CRFs)		X	X	X	X	X	X	X
-----------------------------------	--	---	---	---	---	---	---	---

1. Participants will meet with Nutrition Staff from the NIH Clinical Center to review instructions on keeping a log of their dietary intake at the Screening Visit, to review the intake log at Study Visits 1 and 5, and to receive standard obesity lifestyle management advice at Study Visits 1, 2, 3, 4, and 5.
2. First dose of liraglutide administered at the end of the visit after injection teaching.
3. Interim medical history for changes in health and limited symptom-directed physical examination, including injection sites at visits 2 through 5.
4. Waist circumference measured by Clinical Center Nutrition Staff.
5. Systolic and diastolic blood pressure measured after 5 minutes of rest.
6. Serum or urine pregnancy test (only for women of childbearing potential).
7. Fasting total, HDL- and LDL-cholesterol, triglycerides, fasting plasma glucose concentration

Summary Description:

Prior to Enrollment: The protocol will be explained to the participant and their parent (if the subject is <18 years of age). Research team will preliminarily determine participant's eligibility by inclusion and exclusion criteria over the phone.

Screening Visit: We will obtain informed assent and consent from the participant and their parent/guardian before initiating any research procedures. Each participant will undergo a history and physical examination (measuring weight, height, and blood pressure), and have screening labs drawn, and testing on attention bias to highly palatable images. Female participants will undergo a pregnancy test. Each participant will also answer a series of questionnaires, meet with Nutrition Staff from the NIH Clinical Center to review instructions on keeping a log of their dietary intake, and undergo set-up of a wrist accelerometer to measure free living physical activity. They will also receive material to collect stool at home if they choose to turn in stool samples at Visit 1.

Visit 1:

Each participant will undergo a brief history and directed physical examination at the NIH Clinical Center. Female participants will undergo a pregnancy test. They will then have fasting blood work followed by oral glucose tolerance testing (OGTT), DXA scan, appetite testing, and energy intake measurement at a lunch buffet meal at the NIH Clinical Center. Each participant will have the option to turn in stool samples collected at home or during their clinic visit. They will meet with Nutrition Staff to review their food log, receive standardized education on a healthy diet and physical activity, and measure their waist circumference. The wrist accelerometer will be returned. The participants will receive teaching on administration of subcutaneous study medication and receive their first dose at the end of Visit 1.

Phone Calls 1-3: Each participant will receive three weekly phone calls between Visit 1 and Visit 2 to discuss side effects and dose titration of study drug.

Abbreviated Title: Liraglutide in Teens Post-SG

Version Date: 1/30/23

Visits 2-4: Each participant will undergo a brief history and directed physical examination to include injection site examination at monthly visits. Weight, height, and blood pressure will be measured at each visit. All participants will be assessed for adverse effects of study drug. Female participants will undergo a repeat pregnancy test at every visit. All participants will meet with Nutrition Staff to receive standardized education on a healthy diet. Used 1-month supply of liraglutide pens will be returned to research team and new 1-month supply of liraglutide will be provided to participant. At visit 4, a wrist accelerometer to measure free living physical activity will be placed and testing on attention bias to highly palatable images will be conducted. They will also receive material to collect stool at home if they choose to turn in stool samples at Visit 5.

Visit 5 (at ~16 weeks): Each participant will undergo a history and physical examination and female participants will undergo a pregnancy test. All participants will then undergo fasting blood work followed by 2-hour oral glucose tolerance testing, questionnaires, testing on appetite, DXA scan, and energy intake measurement at a buffet meal at the NIH Clinical Center. They will meet with Nutrition Staff to review their 1-week food log and receive standardized education on a healthy diet and physical activity. Each participant will have the option to turn in stool samples collected at home or during their clinic visit. Used 1-month supply of liraglutide pens will be returned to research team. Liraglutide will be discontinued at this visit. The wrist accelerometer will be returned.

Visit 6 (off medication, at ~28 weeks): Each participant will undergo a history and physical examination. Weight, height, and waist circumference will be measured.

Abbreviated Title: Liraglutide in Teens Post-SG

Version Date: 1/30/23

INTRODUCTION

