1.6.3 Assessment of Potential Risks and Benefits

This clinical drug trial and its associated testing will be associated with some risks which we will try to minimize as outlined below:

-To minimize the risk for gastrointestinal disturbance, liraglutide dosing will be gradually increased over a 5-week period to achieve a maximum dose of 3.0 mg daily. Participants who experience mild to moderate gastrointestinal symptoms will contact the study team and the dose of liraglutide will be decreased and maintained at maximum tolerated dose until completion of the study. Participants who experience severe and/or recurrent gastrointestinal symptoms including acute gallbladder disease will be withdrawn from the study.

Abbreviated Title: Liraglutide in Teens Post-SG

Version Date: 1/30/23

-To minimize the risk for hypoglycemia for participants taking liraglutide, we will exclude patients on insulin or sulfonylurea therapy.

-To minimize the risk of pancreatitis in this study from liraglutide treatment, we will exclude patients with prior history of more than two episodes of pancreatitis as it may put them at higher risk for pancreatitis. If pancreatitis is clinically suspected (either based on signs/symptoms consisting of moderate to severe abdominal pain with nausea or vomiting) the following will take place: 1) Patient will be directed to local emergency department where amylase and lipase levels will be drawn 2) Abdominal ultrasound will be obtained. If a diagnosis of pancreatitis is likely or confirmed based on labs and/or imaging, the following additional actions will be taken. 1) The patient will be recommended for admission for further management or discharged home with supportive care depending on clinical severity. 2) Appropriate treatment will be initiated by primary medical team (usually, NPO and pain medications) if admitted. 3) The patient will be withdrawn from the study. 4) The IRB will be notified per guidelines for serious adverse effects.

-To minimize the risk of kidney failure in this study from liraglutide treatment, we will exclude patients with chronic kidney disease (eGFR <60; eGFR calculated using CKD-EPI equation).

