
 1. To study the effects of 16 weeks of liraglutide 3.0 mg subcutaneously on change in BMI and fat mass in adolescents who underwent vertical sleeve gastrectomy (SG) ≥ 1 year prior to study initiation but still have obesity or have a recrudescence of obesity after surgery. 2. To compare the effects of liraglutide on BMI and fat mass in enrolled participants who had a poor initial response to SG (<20% BMI reduction at BMI nadir) vs. those with a typical post-SG weight loss ($\geq 20\%$ BMI reduction at BMI nadir) 3. Tolerability and Safety of 3.0 mg liraglutide 	
Change from baseline to 16 weeks in:
 
 1. BMI 2. Proportion reducing BMI by at least 5% and 10% 3. BMI standard deviation score for age and sex (BMIZ) 4. Body weight 
Comparison of changes in BMI and fat mass after 16 weeks of liraglutide in participants who had a poor initial response to SG (<20% BMI reduction at BMI nadir) vs. those with a typical post-SG weight loss ($\geq 20\%$ BMI reduction at BMI nadir)
 
Percentage of participants reaching the top liraglutide dose and all adverse events will be recorded.
	
BMI correlates with adiposity and obesity-related comorbidities such as hypertension, type 2 diabetes, sleep apnea, and dyslipidemia.
 
Measuring the proportion of patients reducing their BMI by at least 5% and 10% will help better differentiate degree of weight loss with drug treatment.
 
Percentage total body fat mass by DXA will be measured because weight loss with drug treatment may be associated with changes in body composition.

Tertiary/Exploratory		

 1. To examine the effects of liraglutide in enrolled participants on changes in body composition, metabolic syndrome markers, energy intake, glucose tolerance, GI hormone concentrations, appetite, free living physical activity, mood, 	
 1. Percentage total body fat mass by DXA 2. Appetite score using visual analog scale (VAS) 3. Attention bias to highly palatable images 4. Energy intake at buffet meal 	
Weight loss with drug treatment may affect obesity-related comorbidities/metabolic syndrome markers such as hypertension, dyslipidemia, glucose intolerance/diabetes.
 
We will examine the effect of liraglutide on

Abbreviated Title: Liraglutide in Teens Post-SG

Version Date: 1/30/23

OBJECTIVES	ENDPOINTS	JUSTIFICATION FOR ENDPOINTS

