1.17.2 Dosing and Administration

1.17.2.1 Dose Escalation

Table 1: Titration Schedule for Liraglutide

Study schedule	Week	Liraglutide (subcutaneous injection)
Screening	-1 to 0	-
Baseline visit	0-1	0.6 mg once daily as tolerated
	1-2	1.2 mg once daily as tolerated
	2-3	1.8 mg once daily as tolerated
	3-4	2.4 mg once daily as tolerated
Target study dose	4-16	3.0 mg once daily as tolerated

The participant will start the study drug at Visit 1 (Baseline Visit) after the History & Physical Examination. The study drug will be titrated to the highest tolerable dose as per Table 1 above.

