1.17.2.4 Drug Administration

Prior to first use, Saxenda will be stored in a refrigerator between 36 to 46 degrees Fahrenheit as recommended on its package insert. Participants or their parent will administer first dose of study drug (0.6 mg) subcutaneously at Visit 1 after receiving training from our research team on proper injection technique. They will also be given a medication guide (see document titled, “Saxenda for patients.” Subsequent subcutaneous doses will be administered at participants’ home daily at a consistent time. After first use of the Saxenda pen, the pen will be stored at controlled room temperature (59 to 86 degrees Fahrenheit) or in a refrigerator (36 to 46 degrees Fahrenheit) with the pen cap on.

If a dose is missed, the participant should make up the missed dose on the same day as soon as they remember and take their next daily dose as usual on the following day. The participant should not take an extra dose of the drug or increase their dose on the following day to make up for the missed dose. Any missed doses will be recorded in a patient log.

Participants will call the research team if they miss their dose of study drug for 3 days or more.

The study drug dose will be up-titrated as show in Table 1.

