1.18 PREPARATION/HANDLING/STORAGE/ACCOUNTABILITY

Liraglutide (Brand name Saxenda) will be purchased from Novo Nordisk and stored in the NIH Clinical Center Pharmacy in its original packaging for use as specified in the Package Insert. The NIH Clinical Center Pharmacy will dispense the study medication per study schedule. Study medication will be supplied in 30 days’ supply at Visit 1-4.

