1.27 SAFETY AND OTHER ASSESSMENTS

Adverse events will be monitored via telephone and at all clinic visits using structured case report forms. If any participant develops any concerning adverse events reported by telephone, the individual will be scheduled for an immediate clinic appointment with a trial investigator for further work up, as necessary. Adverse events will also be assessed during the trial via vital signs (blood pressure, heart rate, temperature, respiratory rate), interim history, and the symptom-directed physical examination, as well as by laboratory studies of electrolytes, hepatic, metabolic, and systemic function. There are no EKGs or radiographic assessments for safety.

Physical examination:

Participant's height and weight will be measured; a targeted physical examination (including cardiac, respiratory, gastrointestinal, and neurological assessment) will be performed as part of safety assessment.

Vital signs:

Temperature, pulse, respirations, and blood pressure will be measured as part of safety assessment.

Questionnaires:

Beck depression survey, C-SSR, and Body Esteem Survey will be scored by research team members. The Beck depression survey and C-SSR will be scored on the same day the participant completes the questionnaires. All scores that raise concerns of current suicidality or current major depression will be reported on same day of completion/scoring to [name], NP [name], or [name] who will determine need for follow-up.

Hollingshead Two Factor Index of Socioeconomic Status [85] will be obtained from the participant or parents/guardians of the participant only at baseline.

Injection Site Evaluation and Scoring

Injection sites will be carefully inspected, evaluated, and scored during the study period. The injection site evaluation will include identification and measurement of areas of erythema,

Abbreviated Title: Liraglutide in Teens Post-SG

Version Date: 1/30/23

edema, and induration, as well as the presence of localized pain, tenderness, and itching. A sample injection site evaluation form is included in the Appendix.

In addition, unscheduled evaluations may also be recorded as warranted by clinical conditions, including in the interval between scheduled visits.

Biological specimen collection and laboratory evaluations:

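### The scheduled titration calls end before the step to 3.0 mg, leaving that step 28 days without a scheduled contact on the nominal calendar, against 7 days for each earlier step

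*Combined protocol and SAP*

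**What the plan says.** Section 1.3 (Summary Description) sets the titration contacts: "Each participant will receive three weekly phone calls between Visit 1 and Visit 2 to discuss side effects and dose titration of study drug". It gives no call days. The schedule table lists "Study Visit 2 Day 28 +/- 10 days", with Visit 3 at Day 56 and the same 10-day allowance. No contact is listed between those two visits.

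Table 1 in Section 1.17.2.1 raises the dose weekly: 0.6 mg from week 0, 1.2 mg from week 1, 1.8 mg from week 2, 2.4 mg from week 3 and 3.0 mg from week 4. The text below it reads "The study drug will be titrated to the highest tolerable dose as per Table 1 above". Sections 1.6.3 and 1.7 both describe the titration as lasting 5 weeks.

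Other routes of contact exist. Section 1.6.3: "Participants who experience mild to moderate gastrointestinal symptoms will contact the study team and the dose of liraglutide will be decreased". Section 1.17.2.4: "Participants will call the research team if they miss their dose of study drug for 3 days or more". Section 1.27: "Adverse events will be monitored via telephone and at all clinic visits using structured case report forms". Section 1.17.2.3 lowers the dose by 0.6 mg when intolerable symptoms last beyond 3 days.

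Tolerability and safety of 3.0 mg is a key secondary endpoint. The Objectives and Endpoints table gives its measure: "Percentage of participants reaching the top liraglutide dose and all adverse events will be recorded".

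**The concern.** The calls exist so that staff can ask about side effects and decide on the next increase. They stop before the last increase, the one that reaches the dose under study. The fifth week of the stated 5-week titration, which is the first week at full dose, has no scheduled contact on the nominal calendar.

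Two things are at stake.

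- **Dose management.** The rules work in days. A reduction follows 3 days of intolerable symptoms (Section 1.17.2.3), and a week or more without drug is a ground for discontinuation or withdrawal (Section 1.22). A 28-day interval can outlast both. Intolerance is not rare: the label table in Section 1.17.2.2 gives nausea in 42.4% and vomiting in 34.4% of treated pediatric patients.
- **Adverse-event data.** Section 1.28.4 asks for time of onset and for duration at each severity level. For events just after the top-dose step, these would be recalled about four weeks later unless the participant had called.

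**Working it through.** The plan states no figure for this interval, so there is none to reproduce. The check compares two calendars.

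**Inputs**

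- Dose increases (Table 1): Days 7, 14, 21 and 28.
- Calls (Section 1.3): three, weekly, between Visits 1 and 2. Days 7, 14 and 21 are assumed.
- Visit 2: Day 28, window Days 18 to 38 (21 days). Visit 3: Day 56, window Days 46 to 66.
- Supply (Section 1.18): "Study medication will be supplied in 30 days", that is, 30 days' drug at each of Visits 1 to 4.

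**Formula.** Gap = day of the first scheduled contact strictly after the increase, minus day of the increase.

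**Nominal schedule**

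| Increase to | Day | Next scheduled contact | Gap (days) |
|---|---|---|---|
| 1.2 mg | 7 | Call, Day 14 | 14 − 7 = 7 |
| 1.8 mg | 14 | Call, Day 21 | 21 − 14 = 7 |
| 2.4 mg | 21 | Visit 2, Day 28 | 28 − 21 = 7 |
| 3.0 mg | 28 | Visit 3, Day 56 | 56 − 28 = 28 |

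The last row does not use the assumed call days. The calls must precede Visit 2, so with Visit 2 on or before Day 28 none can follow the Day 28 increase.

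**Visit windows, with 3.0 mg started on Day 28**

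- Visit 2 on Days 18 to 28 (11 of 21 window days): 46 − 28 = 18 to 66 − 28 = 38 days.
- The same, if the drug dispensed at Visit 2 is not stretched past 30 days: Visit 3 is then no later than Day 28 + 30 = 58, so the gap is 18 to 58 − 28 = 30 days.
- Visit 2 on Days 29 to 38 (10 of 21 window days): 29 − 28 = 1 to 38 − 28 = 10 days. There is no long gap.
- Visit 2 on Days 18 to 20 (3 of 21 window days): the 2.4 mg and 3.0 mg steps both come after it, with Visit 3 the next scheduled contact. Three weekly calls starting on Day 7 do not fit before so early a visit. A third call kept on Day 21 would fall on the day of the 2.4 mg step, not after it.

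These are counts of window days, not probabilities.

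**Alternative reading.** If 3.0 mg is started at Visit 2 whatever its date, the gap to Visit 3 runs from 46 − 38 = 8 to 66 − 18 = 48 days across the extremes of the two windows.

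**With one added call near Day 35:** 35 − 28 = 7 days, the same as every earlier step.

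**The case against.** The strongest reply is that a participant who follows the protocol is in touch within days. Mild to moderate gastrointestinal symptoms trigger contact with the team, 3 or more missed days trigger a call, and the dose-reduction rule applies at every dose. The team meets weekly during active treatment, and the safety officer reviews reductions for intolerance (Section 1.38). This is true and narrows the problem to participants who do not report. But these routes either start with the participant, here aged 12 to 20, or carry no date. They were equally available during the earlier steps, where the protocol still scheduled calls.

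Second, on the nominal calendar the top-dose step coincides with an in-person visit at which adverse effects are assessed. That supports counselling and a decision on whether to escalate. It cannot show how 3.0 mg is tolerated.

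Third, Visits 3 to 5 are also about monthly, so four-week recall applies to later events too, and one call does not change that. This stands. So does the point that the documents give no event rates by dose step, so nothing in them shows the last step to be riskier than the others. A later contact also does not alter whether a participant reached 3.0 mg, and no bias in that percentage is claimed.

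Finally, the adverse-event row of the schedule table shows marks only at the start and end of treatment, and these may be the remains of a bar denoting continuous review. Even so, it would set no contact date between Visits 2 and 3. No rule in the protocol requires a check a week after each step, so this is a suggested improvement and not a contradiction in the plan.

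**Conclusion.** The point holds. On the nominal schedule the step to 3.0 mg goes 28 days to its next scheduled contact, against 7 days for each earlier step. The 28 rests on Table 1 and the nominal visit days; the 7s for the 1.2 mg and 1.8 mg steps also assume calls on Days 7, 14 and 21. The gap arises when Visit 2 falls on or before Day 28. It is then 18 to 38 days by the windows, or 18 to 30 if the supply is not stretched. It disappears when Visit 2 is later.

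The consequence is modest. Existing reporting routes cover participants who use them, and neither the primary effect-size calculation nor any planned analysis changes. The gain is in safety follow-up and in the quality of adverse-event records at the dose whose tolerability is a key secondary endpoint. The change is cheap enough to be worth making.

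**What to change.** Tie the contacts to dose increases instead of to Visit 2:

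- Keep the call in the first week of dosing.
- Require one scheduled contact, by telephone or visit, about a week after each increase actually made. This includes the step to 3.0 mg and any delayed step, whatever the date of Visit 2.
- Continue the calls after Visit 2 while increases remain.
- State that these contacts back up participant reporting and do not replace it.

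The cost is a change of wording in Section 1.3 plus, on the nominal schedule, one short call per participant near Day 35: 43 × 1 = 43 calls for the maximum of 43 treated. Early visits or delayed steps add somewhat more, and staff must track the actual dates of increase. Existing staff can make the calls, and that small workload is the downside. Dose, endpoints, sample size and analysis stay as they are.
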